## 9. Risks and Benefits

---

### 9.1. Potential Risks

#### Description of Risk Analysis

Risk Analysis procedures were completed in accordance with ISO 14971:2012. Medtronic has determined the Medtronic TAVR system to be a significant risk medical device. Therefore, Medtronic is sponsoring this clinical study to support approvals for the use of the Medtronic TAVR system to patients with aortic stenosis at low risk for 30-day mortality for SAVR and with bicuspid aortic anatomy.

#### Risks

As with any TAVR procedure, there are risks associated with participation in this study. However, the risks to a patient for participation in this study are not materially different than those a patient would incur if they underwent TAVR outside of this study.

TAVR has been associated with serious complications, including death. In addition, complications may occur at varying intervals necessitating re-intervention or surgical replacement of the TAV. Known complications that may result from TAVR include but are not limited to the following:

- Death
- Cardiac arrest
- Coronary occlusion, obstruction, or vessel spasm (including acute coronary closure)
- Urgent surgery (eg, coronary artery bypass, heart valve replacement, valve explant)
- Multi-organ failure
- Heart failure or low cardiac output
- Myocardial infarction
- Cardiogenic stroke
- Respiratory insufficiency or respiratory failure
- Cardiovascular injury (including rupture, perforation, or dissection of vessels, ventricles, myocardium, or valvular structures that may require intervention)
- Perforation of the myocardium or a vessel
- Stroke or other neurological deficits
- Transient ischemic attack
- Permanent disability
- Urgent need for balloon valvuloplasty (note that BAV during implantation is expected)
- Urgent need for Percutaneous Coronary Intervention (PCI)
- Major or minor bleeding that may or may not require transfusion or intervention (including life-threatening or disabling bleeding)
- Respiratory insufficiency or respiratory failure

- Cardiac tamponade
- Ascending aorta trauma
- Disturbances in the electrical system of the heart that may result in the permanent placement of a device (pacemaker)
  - Atrio-ventricular node block
  - Bundle branch block
  - Asystole
- Cardiac arrhythmias
- Thrombosis (including valve thrombosis)
- Valve migration/embolization
- Ancillary device embolization
- Prosthetic valve dysfunction including but not limited to:
  - Fracture
  - Bending (out-of-round configuration) of the valve frame
  - Under-expansion of the valve frame
  - Calcification
  - Pannus
  - Wear, tear, prolapse or retraction in the valve leaflet
  - Poor valve coaptation
  - Suture breaks or disruption
  - Leak
  - Mal-sizing (prosthesis-patient mismatch)
  - Malposition (either too high or too low)
  - Valve regurgitation (paravalvular or transvalvular)
  - Valve stenosis
    - Mitral valve regurgitation or injury
    - Hypotension or hypertension
    - Renal insufficiency or renal failure (including acute kidney injury)
    - Allergic reaction to antiplatelet agents, contrast medium, or anesthesia
    - Infection (including septicemia or endocarditis)
    - Vascular access site or access related complications, including but not limited to:
      - Dissection
      - Perforation
      - Pain
      - Bleeding
      - Hematoma
      - Pseudoaneurysm
      - Irreversible nerve injury

- Compartment syndrome
- Arteriovenous fistula
- Stenosis
- Tissue erosion
- Encephalopathy
- Pulmonary edema
- Pericardial effusion
- Pleural effusion
- Myocardial ischemia
- Peripheral ischemia
- Bowel ischemia
- Heart murmur
- Hemolysis
- Cerebral infarction-asymptomatic
- Non-emergent reoperation
- Inflammation
- Fever
- Syncope
- Dyspnea
- Anemia
- Angina
- Abnormal lab values (including electrolyte imbalance)
- Exposure to radiation through fluoroscopy and angiography
- Delivery catheter malfunction resulting in need for additional re-crossing of the aortic valve and prolonged procedural time

Each of these complications has the potential to be life-threatening, and some could lead to the need for open heart surgery.

#### **Measures to Mitigate Risks to Study Subjects**

The following measures will be implemented to minimize risks to the study subjects:

- Implanting physicians will have considerable experience with TAVR
- Study sites will have significant experience with surgical SAVR and TAVR
- Patients will undergo thorough imaging assessment during their pre-implant workup
- Patients receiving study device will be followed over the course of the study
- An independent data safety monitoring board (DSMB) will review adverse events and interim results in order to advise Medtronic regarding study conduct, should safety concerns be identified

## Alternatives

Presently, therapeutic alternatives for patients participating in this clinical study include the following:

- Medical therapy
- Balloon aortic valvuloplasty
- Surgical aortic valve replacement

## 9.2. Potential Benefits

The primary potential benefit to subjects participating in the study is restored function of their diseased (stenotic) bicuspid aortic valve. TAVR with the Medtronic TAVR system has been shown to be a safe and effective treatment for patients with symptomatic severe aortic stenosis who are at intermediate risk through extreme risk for operative mortality with SAVR.

## 9.3. Risk-Benefit Rationale

TAVR is now established as a safe and effective treatment option for patients with symptomatic severe aortic stenosis who are at intermediate, high and extremely high risk for surgical aortic valve replacement [2-8]. The Medtronic CoreValve system has been used widely after receiving the CE Mark in 2007, and there is extensive published experience demonstrating the CoreValve system is fulfilling its intended role with a favorable risk/benefit ratio [9-13]. Rigorous clinical studies have established its safety and effectiveness, with improved mortality and quality of life compared with medical therapy in extreme risk patients [6], superiority to SAVR among high operative risk patients [7] and noninferiority to surgery in patients at intermediate surgical risk [8].

The Evolut R and Evolut PRO systems are built upon the same fundamental design principles and mode of operation as the predicate Medtronic CoreValve System. The Evolut R system introduces the feature of recapturability, and the Evolut PRO system builds upon Evolut R and introduces a design feature for reduction of paravalvular regurgitation. A comprehensive protocol of bench and animal testing has indicated the Evolut R and PRO systems are equivalent to the CoreValve system in terms of structural integrity, hydrodynamic performance, and valve durability. Clinical studies of the Evolut R and PRO system have confirmed the safety and efficacy of the Evolut R and PRO systems to be equivalent to the CoreValve system, with no new clinical risks associated [40-42]. Further, no new Zone III risks were identified for patients with bicuspid aortic valve anatomy through Risk Analysis [43].

The risks and benefits of the Medtronic TAVR systems in low risk patients are expected to be similar to those at intermediate through extreme risk for SAVR. The Medtronic TAVR Low Risk IDE trial will evaluate the safety and effectiveness of the Medtronic TAVR systems in tricuspid aortic valve patients with aortic stenosis who are at low predicted risk for mortality with SAVR. This study will be conducted under the Medtronic TAVR Low Risk IDE, and will evaluate the procedural safety and efficacy of Medtronic TAVR (Evolut PRO system and Evolut R system) in patients with severe bicuspid aortic valve stenosis who are at low predicted risk of mortality with SAVR.

Although there are risks to the subjects for participation in the study, they are anticipated to be similar to the risks of undergoing TAVR outside of the study. The potential benefits outweigh the design and use-related risks established through risk analysis.

## 10. Adverse Events and Device Deficiencies

Definitions for Adverse Events, Adverse Device Effects, and Device Deficiencies are provided below.

### 10.1. Definitions/Classifications

#### 10.1.1. Definitions

The definitions to be applied for the purposes of reporting adverse events are provided in Table 5.

**Table 5. Adverse event definitions for reporting requirements**

Event Type	Definition
Adverse Event (AE)  (ISO14155:2011 3.2)	Any untoward medical occurrence, unintended disease or injury, or untoward clinical signs (including abnormal laboratory findings) in subjects, users or other parties, whether or not related to the investigational medical device (47) NOTE 1: This definition includes events related to the investigational medical device or the comparator. NOTE 2: This definition includes events related to the procedures involved. NOTE 3: For users or other parties, this definition is restricted to events related to investigational medical devices.
Serious Adverse Event (SAE)  (ISO14155:2011 3.37)	Adverse event that a) led to death, b) led to a serious deterioration in the health of the subject, resulting in 1) a life-threatening illness or injury, or 2) a permanent impairment of a body structure or a body function, or 3) in-patient or prolonged hospitalization, or 4) medical or surgical intervention to prevent life-threatening illness or injury or permanent impairment to a body structure or a body function, c) led to fetal distress, fetal death or a congenital abnormality or birth defect (47). NOTE: Planned hospitalization for a pre-existing condition, or a procedure required by the CIP, without serious deterioration in health, is not considered a serious adverse event.
Adverse Device Effect (ADE) or Device Related Adverse Event (ISO14155:2011 3.1)	Adverse event related to the use of an investigational medical device. NOTE 1: This definition includes adverse events resulting from insufficient or inadequate instructions for use, deployment, implantation, installation, or operation, or any malfunction of the investigational medical device (47). NOTE 2: This definition includes any event resulting from an error use or from intentional misuse of the investigational medical device.
Serious Adverse Device Effect (SADE) (ISO14155:2011 3.36)	Adverse device effect that has resulted in any of the consequences characteristic of a Serious Adverse Event (47, 48).
Unanticipated Adverse Device Effect	Any serious adverse effect on health or safety of a patient, or any life-threatening problem or death caused by or associated with the device, if the effect, problem, or

(UADE) (21 CFR 812.3)	death has not been previously identified in nature, severity, or degree of incidence in the investigational plan or application, (including a supplementary plan or application), or any other unanticipated serious problem associated with a device that relates to the rights, safety, or welfare of subjects (49).
--------------------------	--

## 10.2. Reporting of Adverse Events

### 10.2.1. Evaluation and Documentation of Adverse Events and Device Deficiencies

Investigators are required to evaluate and document in the subject's medical records all adverse events (AE) and device deficiencies (per the definitions in Table 5) observed in study subjects from the time they are enrolled until they are exited from the study. All AE should be followed through their resolution or until subject's study exit.

All AEs that occur during the study need to be reported to Medtronic via the AE eCRF. Documented pre-existing conditions are not considered to be reportable unless there is a change in the nature or severity of the condition. Pre-existing events should be reported as AE in the situation where a new treatment has to be started or an existing treatment has to be changed to treat the adverse event and the event is accompanied with signs and symptoms. In addition, after the subject has completed his/her two-year follow-up visit, only SAEs and device-related AEs need to be reported to Medtronic.

Unavoidable events are conditions which do not fulfill the definition of an Adverse Event, meaning those medical occurrences, clinical signs (including abnormal laboratory findings), diseases or injuries that are not untoward in nature; specifically, those resulting from the intended injury such as the index TAVR procedure. The events listed in Table 6 are expected for patients undergoing TAVR, and do not need to be reported as AE, unless they occur outside of the stated timeframe, are otherwise considered to be an AE according to the treating investigator, or are suspected or confirmed to be device-related.

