#### Additional Outcome Measures

Additional outcome measures are listed below.

1. All-cause mortality at one year, and annually through 10 years
2. All stroke (disabling and non-disabling) at one year, and annually through 10 years
3. New permanent pacemaker implantation at 30 days
4. Myocardial infarction at 30 days
5. Life-threatening bleeding at 30 days, one year, and annually through 10 years
6. Prosthetic valve endocarditis at 30 days, one year, and annually through 10 years
7. Prosthetic valve thrombosis at 30 days, one year, and annually through 10 years
8. Valve-related dysfunction requiring repeat procedure at 30 days, one year, and annually through 10 years
9. Repeat hospitalization for aortic valve disease at 30 days, one year, and annually through 10 years
10. Repeat hospitalization for ascending aorta disease at 30 days, one year, and annually through 10 years
11. Hemodynamic performance metrics by Doppler echocardiography
  - Mean aortic gradient at baseline, 30 days, one year, annually through 5 years and at years 7 and 10
  - Effective orifice area at baseline, 30 days, one year, annually through 5 years and at years 7 and 10
  - Degree of total, peri, and transvalvular prosthetic regurgitation at baseline, 30 days, one year, annually through 5 years and at years 7 and 10
12. New York Heart Association (NYHA) functional classification at baseline, 30 days, one year and annually through 5 years and at years 7 and 10  
NYHA function classification will be reported as proportions at each specified time point.
13. Health-related quality of life as assessed by

- Kansas City Cardiomyopathy (KCCQ) instrument at baseline, 30 days, one year, annually through 5 years
- EQ-5D survey at baseline, 30 days and one year

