**1.0 Safety Endpoints (continued)**

Stroke and TIA

Diagnostic criteria
 
1) Acute episode of a focal or global neurological deficit with at least 1 of the following:
 
 
• change in the level of consciousness
 
• hemiplegia, hemiparesis
 
• numbness or sensory loss affecting 1 side of the body
 
• dysphasia or aphasia
 
• hemianopia
 
• amaurosis fugax
 
• other neurological signs or symptoms consistent with stroke
 
 
Stroke: duration of a focal or global neurological deficit <math>\geq 24</math> h; OR <math>< 24</math> h if available neuroimaging documents a new hemorrhage or infarct; OR the neurological deficit results in death
 
TIA: duration of a focal or global neurological deficit <math>< 24</math> h, any variable neuroimaging does not demonstrate a new hemorrhage or infarct
 
2) No other readily identifiable non-stroke cause for the clinical presentation (eg, brain tumor, trauma, infection, hypoglycemia, peripheral lesion, pharmacological influences), to be determined by or in conjunction with the neurologist
 
3) Confirmation of the diagnosis by at least 1 of the following:
 
 
• Neurologist or neurosurgical specialist
 
• Neuroimaging procedure (CT scan or brain MRI), but stroke may be diagnosed on clinical grounds alone
 

Stroke Definitions
 
Disabling stroke: an mRS score of 2 or more at 90 days and an increase in at least 1 mRS category from an individual’s pre-stroke baseline
 
Non-disabling stroke: an mRS score of <math>< 2</math> at 90 days or one that does not result in an increase in at least 1 mRS category from an individual’s pre-stroke baseline

Stroke Classifications
 
Ischemic: an acute episode of focal cerebral, spinal, or retinal dysfunction caused by infarction of the central nervous system tissue
 
Hemorrhagic: an acute episode of focal or global cerebral or spinal dysfunction caused by intraparenchymal, intraventricular, or subarachnoid hemorrhage
 
Undetermined: insufficient information to allow categorization as ischemic or hemorrhagic

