## 2.0 Other Related Complications (continued)

Complication	Definition
Conversion to open surgery	Conversion to open sternotomy during the TAVR procedure secondary to any procedure-related complications
Unplanned use of cardiopulmonary bypass	Unplanned use of CPB for hemodynamic support at any time during the TAVI procedure
Coronary artery obstruction	Angiographic or echocardiographic evidence of a new, partial or complete, obstruction of a coronary ostium, either by the TAV prosthesis itself, the native leaflets, calcifications, or dissection, occurring during or after the TAVR procedure.
Ventricular septal perforation	Angiographic or echocardiographic evidence of a new septal perforation during or after the TAVR procedure
Mitral valve apparatus damage or dysfunction	Angiographic or echocardiographic evidence of new damage (chordae, papillary muscle, or leaflet) to the mitral valve apparatus or dysfunction (eg, restrictions due to the TAV of the mitral valve during or after the TAVR procedure
Cardiac tamponade	Evidence of new pericardial effusion associated with hemodynamic instability and clearly related to the TAVI procedure
Prosthetic valve thrombosis	Any thrombus attached to or near an implanted valve that occludes part of the blood flow path, interferes with valve function, or is sufficiently large to warrant treatment. Valve-associated thrombus identified at autopsy in a patient whose cause of death was not valve related should not be reported as valve thrombosis.
Valve migration	After initial correct positioning, any observed movement (upward or downward) of the TAV within the aortic annulus from its initial position, with or without consequences.
Valve embolization	The TAV moves during or after deployment such that it loses contact within the aortic annulus
Ectopic valve deployment	Permanent deployment of the TAV in a location other than the aortic root
TAV in TAV deployment	Additional valve prosthesis is implanted within a previously implanted TAV because of sub-optimal device position and/or function, during or after the index procedure.
Hemolysis	Red cell destruction confirmed by lab data Minor hemolysis: No intervention required Major hemolysis: Requires intervention (eg, iron supplements, transfusion, invasive intervention).

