7.9.3. Additional Outcome Measures

1. All-cause mortality at one year, and annually through 10 years

Event rate estimates will be provided at 1 year and annually thereafter up to 10 years for the attempted implant set. The outcome is descriptive including Kaplan-Meier rates and no statistical hypothesis test is specified.

2. All stroke (disabling and non-disabling) at one year, and annually through 10 years

Event rate estimates will be provided at 1 year and annually thereafter up to 10 years for the attempted implant set. The outcome is descriptive including Kaplan-Meier rates and no statistical hypothesis test is specified.

3. New permanent pacemaker implantation at 30 days

Event rate estimates will be provided at 30 days for the attempted implant set. The outcome is descriptive including Kaplan-Meier rates and no statistical hypothesis test is specified.

4. Myocardial Infraction at 30 days

Event rate estimates will be provided at 30 days for the attempted implant set. The outcome is descriptive including Kaplan-Meier rates and no statistical hypothesis test is specified.

5. Life-threatening bleeding at 30 days, one year, and annually through 10 years

Event rate estimates will be provided at 30 days, 1 year and annually thereafter up to 10 years for the attempted implant set. The outcome is descriptive including Kaplan-Meier rates and no statistical hypothesis test is specified.

6. Prosthetic valve endocarditis at 30 days, one year, and annually through 10 years

Event rate estimates will be provided at 30 days, 1 year and annually thereafter up to 10 years for the attempted implant set. The outcome is descriptive including Kaplan-Meier rates and no statistical hypothesis test is specified.

7. Prosthetic valve thrombosis at 30 days, one year, and annually through 10 years

Event rate estimates will be provided at 30 days, 1 year and annually thereafter up to 10 years for the attempted implant set. The outcome is descriptive including Kaplan-Meier rates and no statistical hypothesis test is specified.

8. Valve-related dysfunction requiring repeat procedure at 30 days, one year, and annually through 10 years

Event rate estimates will be provided at 30 days, 1 year and annually thereafter up to 10 years for the attempted implant set. The outcome is descriptive including Kaplan-Meier rates and no statistical hypothesis test is specified.

9. Repeat hospitalization for ascending aorta disease at 30 days, one year, and annually through 10 years

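### After the two-year visit, a non-disabling stroke that is neither serious nor device-related need not be reported, although all stroke is an outcome through year 10

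*Protocol*

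**What the plan says.** Protocol section 10.2.1 opens with a general rule: "All AEs that occur during the study need to be reported to Medtronic via the AE eCRF". The same paragraph then narrows it: "after the subject has completed his/her two-year follow-up visit, only SAEs and device-related AEs need to be reported to Medtronic". No exception is made for events that are study outcomes.

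Protocol section 4.1 lists as an additional outcome "All stroke (disabling and non-disabling) at one year, and annually through 10 years". SAP section 7.9.3 repeats it, with Kaplan-Meier rates in the attempted implant set. Valve thrombosis is also followed to year 10: "Prosthetic valve thrombosis at 30 days, one year, and annually through 10 years".

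Protocol section 11.1 sets the CEC's minimum workload as deaths and safety-endpoint events that investigators have reported, and bases the safety analysis on adjudicated events. SAP section 7.2 censors a subject without a recorded event at the last date on which anything was recorded for that subject. SAP section 7.4 provides for no imputation unless otherwise specified.

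**The concern.** Up to the two-year visit, every stroke is reported because every adverse event is. After it, a stroke must be reported only if it is serious or device-related. The outcome itself does not change at year 2: it still counts all strokes. Eight of the ten annual time points (years 3 to 10) therefore fall partly under the narrower rule.

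Any loss goes one way. An unreported stroke removes an event and leaves the subject in the risk set as event-free, so the cumulative all-stroke rate can only be too low. At stake are the long-term stroke rates in the final report.

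**Working it through.** The plan states no figure on this point, so there is nothing to reproduce. The check has two parts.

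**1. Can a protocol-defined stroke miss both reporting routes?**

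- *Outcome definition (Protocol Appendix V, section 1.0).* A stroke is non-disabling if the modified Rankin score (mRS) is below 2 at 90 days, "or one that does not result in an increase in at least 1 mRS category". Seriousness is not required.
- *Serious route (Protocol Table 5).* An event is serious if it leads to death, threat to life, permanent impairment of structure or function, "in-patient or prolonged hospitalization", or intervention to prevent such harm. Stroke is not serious by default.
- *Device route (Protocol Table 5).* The definition is "Adverse event related to the use of an investigational medical device". A late stroke attributed to another cause does not qualify.

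So a mild stroke after year 2, managed without admission, with no permanent impairment, needing no preventive intervention and judged unrelated to the device, meets the outcome definition and neither reporting route.

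The same test for valve thrombosis gives a different answer. Appendix V, section 2.0 defines it as "Any thrombus attached to or near an implanted valve that occludes part of the blood flow path, interferes with valve function", or large enough to warrant treatment. The event code list places it among TAVR-related complications. Appendix V, section 4.0 assigns cases of unassessable relatedness to the possible category. It would normally stay reportable as device-related, serious or not. The open question is that the protocol has five causality levels and does not say which of them count as device-related.

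**2. How large could the stroke loss be?**

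The annual stroke hazard *h* and the share *m* of strokes after year 2 that are neither serious nor device-related are assumptions; neither is in the documents. The hazard is taken as constant, with no competing death or dropout, and reporting as complete to year 2.

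- True 10-year rate = 1 − exp(−10*h*)
- Observed 10-year rate = 1 − exp(−[2*h* + 8*h*(1 − *m*)])

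Worked case, *h* = 0.02 and *m* = 0.10: true = 1 − exp(−0.200) = 18.1%. Observed = 1 − exp(−[0.040 + 0.144]) = 1 − exp(−0.184) = 16.8%. The difference is 1.32 points, and 0.0132 × 150 = 2.0 subjects.

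| *h* per year | *m* | True | Observed | Difference (points) | Subjects of 150 |
|---|---|---|---|---|---|
| 1% | 10% | 9.5% | 8.8% | 0.73 | 1.1 |
| 1% | 30% | 9.5% | 7.3% | 2.20 | 3.3 |
| 2% | 5% | 18.1% | 17.5% | 0.66 | 1.0 |
| 2% | 10% | 18.1% | 16.8% | 1.32 | 2.0 |
| 2% | 30% | 18.1% | 14.1% | 4.03 | 6.0 |
| 3% | 10% | 25.9% | 24.1% | 1.80 | 2.7 |
| 3% | 30% | 25.9% | 20.4% | 5.53 | 8.3 |

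With *m* = 0 the difference is zero at every hazard. Death and dropout would lower the subject counts.

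**The case against.** The strongest reply is that other parts of the protocol continue collection with no year-2 limit:

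- Section 8.8 has any adverse event documented at each follow-up interval, by telephone at years 6, 8 and 9, and the section 8.1 schedule lists adverse events through year 10.
- Section 8.1 also calls for an mRS one and three months after a suspected or confirmed stroke, with no end date.
- Section 10.2.1 has details of every observed event entered on the adverse event form, and asks for source documents on all endpoint-related events for adjudication.
- Section 10.2.3 requires adverse events during the study to be reported on the electronic form.

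This stands to a large extent. A reader might infer that ascertainment as a whole drops at year 2, or that the CEC never sees the affected strokes. The documents do not support either: detection and site records continue, and the source-document instruction is not time-limited. What narrows is mandatory reporting to the sponsor. The reply does not remove the gap, however. The narrowing sentence is the specific one and says *only*, a site may reasonably follow it, and the request for source documents does not itself order an event report. If the sponsor intends the wider reading, the sentence contradicts it.

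A second reply is that few strokes would escape. Many lead to admission. One with a deficit under 24 hours that is not fatal counts as a stroke only if imaging shows a new infarct or hemorrhage, which could be read as structural impairment and hence serious. This also stands, and it is why the range above starts at zero.

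A third reply is that these outcomes are descriptive, with no hypothesis test. That is correct and limits the consequence to the accuracy of the reported late rates.

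**Conclusion.** The point holds for stroke, as a narrow gap in mandatory reporting and an unreconciled inconsistency within the protocol. A non-disabling stroke after the two-year visit that is neither serious nor device-related need not be reported, may not be adjudicated, and would then leave the subject counted as event-free. The all-stroke rates for years 3 to 10 can be biased downward.

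The size is not determinable from the documents. Under the assumed ranges it is 0 to 5.5 points at 10 years; it may be near zero if almost all late strokes are treated as serious.

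A reader might extend the point to valve thrombosis, but that is exposed only if device-related is read to exclude possibly related events. Most other listed outcomes would ordinarily be serious or device-related and so remain reportable. Nor do the documents show that the stroke curve will visibly flatten after year 2. The 30-day primary safety endpoint and device success are unaffected. This is a minor point, worth correcting because the correction is cheap.

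**What to change.** Amend the sentence in Protocol section 10.2.1 to the following effect: after the two-year visit, sites report through year 10 all SAEs, all device-related adverse events, and any event that may meet an outcome listed in section 4.1 with time points to 10 years, at minimum every suspected or confirmed stroke, whatever its seriousness or relatedness.

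In the same edit:

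- State which of the five causality levels in Appendix V, section 4.0 count as device-related for this rule. This settles valve thrombosis.
- Reconcile the sentence with section 8.8, with the adverse event form and source-document instructions in section 10.2.1, and with section 10.2.3, so that all sites apply one rule.

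Refer to section 4.1 for the outcome list, because Appendix V does not define the rehospitalization outcomes.

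The cost is a short protocol amendment and a handful of extra event forms and adjudications. The primary analysis does not change.
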